
	
Plasma exposure to lurbinecetin:
 
Only patients who completed the study with sufficient and interpretable PK parameters will be included in the statistical comparison of plasma exposure to lurbinecetin. Descriptive statistics will be used to summarize pharmacokinetic data.
 
The primary parameter of interest for the statistical analysis will be plasma dose-adjusted <math>AUC_{(0-\infty)}</math> (if data do not permit so, <math>AUC_{(0-t)}</math> will be used) of lurbinecetin. The analysis will compare the log-transformed AUC for lurbinecetin administered in combination with itraconazole (Test) to the lurbinecetin alone (Reference). A mixed-effects model will be fit to the data with log-transformed AUC as the dependent variable, treatment (Test or Reference), period and sequence as fixed effects, and patient (sequence) as a random effect. The estimated least square means and intrasubject variability from the mixed-effects model will be used to construct 90% CIs for the difference in means on the log scale between treatments (Test or Reference). The adjusted mean differences and the 90% CIs will be exponentiated to obtain estimates of the ratio of adjusted geometric means (Test/Reference) and 90% CIs for the ratios.
 
A large difference (e.g. two-fold difference shown from CIs and least square means) will be considered to show evidence on whether itraconazole co-administration has a clinically relevant effect on lurbinecetin exposure.
 
Secondary PK parameters:
 
Similar models used for the primary endpoint will be fit to the data with dose-normalized <math>AUC_{(0-t)}</math> and <math>C_{max}</math> and in <math>Cl</math>, <math>V_{ss}</math> and <math>T_{1/2}</math> of lurbinecetin or metabolite to parent exposure PK parameters ratio, as the dependent variable. Results will also be assessed graphically.
 
Plasma protein binding:
 
A similar model used for the primary endpoint will be fit to the data with dose-normalized <math>AUC_u</math> as the dependent variable.
 
Safety:
 
Descriptive statistics will be used to characterize the profiles of drug-related AEs, drug-related deaths, SAEs, clinical laboratory data, drug-related delays and/or treatment discontinuations. All AEs will be graded according to NCI-CTCAE v.5. Tables will be displayed by study part, sequence and treatment (Test or Reference).
 
Pharmacogenetics:
 
Descriptive statistics will be used to summarize pharmacogenetic data at the time of planned analysis.

PLANNED TRIAL PERIODS (individually per patient)	
Patients will be evaluated at scheduled visits in three study periods:
 
 
• Pre-treatment (screening): from signature of the ICF to the day of first administration of the study treatment (itraconazole or lurbinecetin).
 
• Treatment: from first administration of the study treatment (itraconazole or lurbinecetin) to the last dose of lurbinecetin plus 31 days (end-of-treatment, EOT) (maximum of three cycles).
 
• Follow-up: after EOT, patients with treatment-related toxicities
 

[figure not shown]
	
> grade 2 will be followed every four weeks until recovery to at least grade 1 or stabilization of all treatment-emergent AEs, or until the start of a new antitumor therapy, until the continuation of treatment outside this study under a Compassionate Use Agreement or death, whichever occurs first.
 
Patients will be considered to be on-study from the signature of the ICF to the end of the follow-up period. Patients will be considered to be on-treatment for the duration of their treatment and until the day of EOT, immediately before the start of the follow-up period.
 
An end-of-treatment (EOT) visit will be performed within 31 days (<math>\pm 10</math> days) after administration of the last dose of lorbinecetin, unless the patient dies or starts any new antitumor therapy outside this clinical study, in which case the EOT visit should be performed immediately before the start of the new therapy (ideally the day before or the same day).

PLANNED TRIAL PERIODS (for the whole study)	
The total duration of the study will be approximately 22 months, including approximately an 18-month enrolment period.
 
Planned start date (first patient on study): 3Q2020.
 
Planned enrollment period: approximately 18 months.
 
Planned end-of-study date (clinical cutoff): 31 (<math>\pm 10</math>) days after the date of the last lorbinecetin administration for last patient/last cycle, or when confirmation of evaluability of at least eight patients in Part B, whichever occurs last.
 
Patients who meet the continuation criteria and obtain a clear clinical benefit with lorbinecetin after the completion of the first two study cycles, according to the Investigator's criteria may continue treatment outside this study under a Compassionate Use Agreement after the completion of the optional third study cycle. Should the patient continue under a Compassionate Use Agreement, the treating center must request authorization to the relevant Health Authorities and notify the Sponsor in due time.

## SCHEMATIC OF TRIAL DESIGN

**Part A and Part B, sequence 1 (TR)**

**Part B, sequence 2 (RT)**

\* Depending on PK results of Part A.

### Home-based procedure

### ↓ Patient's diary and itraconazole delivery

↓ Itraconazole p.o  
administration

↓ Lurbinectedin i.v. infusion      ↑ PK sampling

↑ PK sampling

\* Depending on PK results of Part A.

C, cycle; D, day; h, hour; PK, pharmacokinetics; RT, reference-test sequence; TR, test-reference sequence.

## SCHEDEULE OF ASSESSMENTS AND PROCEDURES

### STUDY PART A AND PART B SEQUENCE 1 (TR):

Study Period►	Screening (days prior to registration)	Cycle 1															Cycle 2							Cycle 3	End of Treatment	Follow-up AEs	
		-4	-3	-2	-1	1*	2	3	4	5	6	7	8	11	15	1	2	3	5	8	11	15	1	31 (±10)			
Written IC	(Before any study procedure)	-	-	-	-	-	-	-	-	-	-	-	-	-	-	-	-	-	-	-	-	-	-	-	-	-	
Demographic data	-14	-	-	-	-	-	-	-	-	-	-	-	-	-	-	-	-	-	-	-	-	-	-	-	-	-	
Medical history/Baseline condition	-14	-	-	-	-	-	-	-	-	-	-	-	-	-	-	-	-	-	-	-	-	-	-	-	-	-	
Primary diagnosis/Prior treatment(s)	-14	-	-	-	-	-	-	-	-	-	-	-	-	-	-	-	-	-	-	-	-	-	-	-	-	-	
Complete physical examination, including weight, height and BSA a	-14	-	-	-	-	X	-	-	-	-	-	-	-	-	-	X	-	-	-	-	-	-	X	X	-	-	
ECOG PS a	-14	-	-	-	-	X	-	-	-	-	-	-	-	-	-	X	-	-	-	-	-	-	X	X	-	-	
Vital signs (HR, BP, T) a	-14	-	-	-	-	X	-	-	-	-	-	-	X	-	-	X	-	-	-	X	-	-	X	-	-	-	
Hematology b	-14	-	-	-	-	X	-	-	-	-	-	X	-	X	X	-	-	-	X	-	X	X	X	X	-	-	
Coagulation (INR) c	-14	-	-	-	-	X	-	-	-	-	-	-	-	-	-	-	-	-	-	-	-	-	-	-	-	-	
Biochemistry-A b	-14	-	-	-	-	X	-	-	-	-	-	X	-	X	X	-	-	-	X	-	X	X	X	X	-	-	
Biochemistry-B b	-14	-	-	-	-	X	-	-	-	-	-	-	-	-	X	-	-	-	-	-	-	-	X	X	-	-	
Calculated CLcr (Cockcroft and Gault's formula) b, d	-14	-	-	-	-	X	-	-	-	-	-	X	-	X	X	-	-	-	X	-	X	X	X	X	-	-	
Detection of SARS-CoV-2 (COVID-19) by PCR	-14	-	-	-	-	-	-	-	-	-	-	-	-	-	-	-	-	-	-	-	-	-	-	-	-	-	
Pregnancy test (serum β-hCG) (only if the patient is a WOCBP)	-14	-	-	-	-	X	-	-	-	-	-	-	-	-	-	X	-	-	-	-	-	-	X	X	-	-	
ECG e	-14	-	-	-	-	X	-	-	-	-	-	-	-	-	-	X	-	-	-	-	-	-	-	-	X	-	-
LVEF (by ECHO or MUGA) f	-14	-	-	-	-	-	-	-	-	-	-	-	-	-	-	-	-	-	-	-	-	-	-	-	-	-	
Randomization g	-14	-	-	-	-	-	-	-	-	-	-	-	-	-	-	-	-	-	-	-	-	-	-	-	-	-	
Itraconazole delivery and patient's diary h	-	-	-	-	-	-	-	-	-	-	-	-	-	-	-	-	-	-	-	-	-	-	-	-	-	-	
Prophylactic medication i	-	-	-	-	-	X	-	-	-	-	-	-	-	-	-	X	-	-	-	-	-	-	X	-	-	-	
Lurbinectedin 1h (-5/+20 min) infusion	-	-	-	-	-	X	-	-	-	-	-	-	-	-	-	X	-	-	-	-	-	-	X	-	-	-	
Itraconazole oral administration	-	X	X	X	X	X j	X	X	X	X	X	X	X	X	X	-	-	-	-	-	-	-	-	-	-	-	
Contact to patients (via telephone or other) k	-	X	X	X	X	-	X	X	X	X	X	X	X	X	X	-	-	-	-	-	-	-	-	-	-	-	

Study Period►	Screening (days prior to registration)	Cycle 1													Cycle 2						Cycle 3		End of Treatment	Follow-up AEs		
		-4	-3	-2	-1	1*	2	3	4	5	6	7	8	11	15	1	2	3	5	8	11	15	1	31 (±10)		
Cycle Day►		-	-	-	-	X	-	-	-	-	-	-	-	-	X	-	-	-	-	-	-	-	-	-	-	-
AAG blood sample collection	-	-	-	-	-	X	-	-	-	-	-	-	-	-	X	-	-	-	-	-	-	-	-	-	-	
IL6 blood sample collection	-	-	-	-	-	X	-	-	-	-	-	-	-	-	X	-	-	-	-	-	-	-	-	-	-	
PGt blood sample collection (only if written IC given) 	-	-	-	-	-	One blood sample collected at any time during the study, but preferably just before lorbinecetin treatment start in Cycle 1																	-	-		
Lorbinecetin PK blood sample collection m	-	-	-	-	-	X	X	X	-	X	-	-	X	X	X	X	X	X	X	X	X	X	-	-	-	
Itraconazole PK blood sample collection m	-	-	-	-	-	X	X	-	-	-	-	-	X	-	-	-	-	-	-	-	-	-	-	-	-	
AEs n		Continuous o																							X p	
Intercurrent events, concomitant disease and therapies		continuous																							-	

Registration = confirmation of eligibility and inclusion; Day 1 = the day of lorbinecetin administration (with infusion start) of cycle 1 or 2; Day 8 = seven days after the lorbinecetin administration of cycle 1 or 2 (±2 days); Day 15 = fourteen days after the lorbinecetin administration of cycle 1 or 2 (±2 days).

**\* Permitted windows for assessments before Day 1 of Cycle 1:**

If physical examination, ECOG PS, vital signs, Hematology, Biochemistry-A, Biochemistry-B, CLcr (provided only if serum creatinine levels are above ULN) and Coagulation were assessed >10 days before Day 1 of Cycle 1, the tests must be repeated the day before or the Day 1 (always prior to lorbinecetin infusion).

If pregnancy test was done >7 days before Day 1 of Cycle 1, the test must be repeated the day before or the Day 1 (always prior to lorbinecetin infusion).

A patient should only be treated if eligibility criteria are still met according to assessments performed closest to treatment start.

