**Permitted windows for assessments after Day 1 of Cycle 1:**

A ± 2-day time window will be allowed for Hematology, Biochemistry-A and CLcr (provided only if serum creatinine levels are above ULN) on Day 8 and Day 15, and for vital signs on Day 8 of Cycle 1.

A -1 day window will be allowed for physical examination, ECOG PS, vital signs, Hematology, Biochemistry-A, and Biochemistry-B, CLcr (provided only if serum creatinine levels are above ULN) and Pregnancy test on Day 1 of Cycle 2 and further cycles (always prior to lorbinecetin infusion).

A + 2 days window for Day 1 lorbinecetin administration of Cycle 3.

If a drug administration is delayed beyond the permitted protocol window, assessments planned for the original administration day must be repeated on the day the dose is finally administered.

a Should treatment be administered more than ten days after the screening tests, repeat these tests prior to the first infusion and if clinically indicated. Height needs to be measured at baseline only. BSA will not be reported at the EOT. BSA calculated according to DuBois formula (see [Appendix 4](#)).

b Any patient having any grade ≥ 3 laboratory abnormalities and/or treatment-related AEs is suggested to have the relevant tests re-assessed at intervals of at least 72 hours but not more than one week until recovery to at least grade 2 has been documented.

c Repeat during treatment period and at EOT if clinically indicated.

d Calculated CLcr [Cockcroft and Gault's formula] should be provided only if serum creatinine levels are above ULN.

e ECG should be done in triplicate (at screening, Day 1 and at EOT visit) and allow rhythm definition (at least 30 seconds of duration), PR interval and QT interval (raw and corrected by HR using Bazett's formula). On Day 1, 5 minutes before SOI (-25 to -1 min before preinfusion PK samples collection) and 1 hour after EOI (-15 to -1 min before the PK sample collection), both will be done in triplicate.

f A previous LVEF assessment could be used if was made within 28 days prior to screening and during treatment period and at EOT will be repeated only if clinically indicated.

g Randomization apply for study Part B only.

h Itraconazole for self-administration and the patient's diary should be given to the patient on Day -5 with a -2/+1 day time window (i.e., from Day -7 to Day -4).

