## 6.2 PATIENT REGISTRATION

Eligibility will be checked before registration confirmed by the Sponsor. The patient will be a screening failure if not all inclusion criteria are met, if any exclusion criterion is met, or if the Sponsor does not approve registration. Regardless of circumstances, Investigators will not be allowed to treat any patient before appropriate receipt of the Sponsor's agreement to proceed with registration. A patient should only be treated if eligibility criteria are still met according to assessments performed closest to first drug administration.

A patient who has been treated without the Sponsor's agreement may not be considered evaluable for the primary endpoint of the study and may need to be replaced (although can continue in treatment provided this does not pose a risk to the patient until discontinuation for any other reason).

For patients included in the study (all registered patients) but never treated, only baseline and off-study visit modules of the eCRF should be completed but serious adverse events (SAEs) occurring during screening need to be reported (using paper SAE forms).

For screen failures (patients who started screening but were not finally registered), only the screening form of the eCRF should be completed but SAEs occurring during screening need to be reported (using paper SAE forms).

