## **7.2 ADMINISTRATION OF THE STUDY MEDICATION**

### **Itraconazole**

Itraconazole will be administered orally once daily as 200 mg (2 capsules of 100 mg).

In the co-administration cycles, itraconazole will be administered orally once daily in the morning after breakfast during 12 consecutive days, self-administered at home from Day -4 (i.e., four days before lurbinectedin infusion) until Day 8 (i.e., seven days after lurbinectedin infusion), and supplied at the study center on Day 1, following recommendations at the Summary of Product Characteristics (SmPC). On Day 1 (i.e., day of lurbinectedin infusion), itraconazole will be given immediately prior to the start of the lurbinectedin infusion. In fact, itraconazole should be administered after obtaining the itraconazole PK sample #1 and before the start of lurbinectedin infusion (-15 min to -1 min). In case of lurbinectedin delay ( $\leq 2$  days), itraconazole could be administered during a maximum of 14 days.

In Sequence 1 (TR), itraconazole for self-administration and the patient's diary should be given to the patient on Day -5 with a -2/+1 day time window (i.e., from Day -7 to Day -4). In Sequence 2 (RT), itraconazole and the patient's diary should be given to the patient on Day -5 of Cycle 2 with a -2/+1 day time window (i.e., from Day 15 of Cycle 1 to Day -4 of Cycle 2).

In addition, the study center will contact the patients (via telephone or other methods) daily during itraconazole intake to remind them or confirm that they have taken the morning dose of itraconazole when they are not at the study center.

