#### **7.4 CRITERIA FOR TREATMENT CONTINUATION**

Patients may continue treatment with lorbinecetin as long as no unacceptable toxicity and/or PD occurred, and for a maximum of three cycles. Thereafter, treatment with lorbinecetin can continue under a Compassionate Use Agreement.

**In Part A and Part B, patients assigned to Sequence 1 (TR) (lorbinecetin + itraconazole in Cycle 1),** after Cycle 1 the administration of a new cycle should be delayed if the criteria in [Table 7](#) are not met on the corresponding Day 1. Re-assessments will be performed periodically at intervals of at least 72 hours but not more than one week. Lorbinecetin administration should be delayed until recovery of these parameters. A maximum delay of 14 days from the theoretical due date will be allowed for recovery from treatment-related AEs. If recovery has not occurred after that period, the patient should discontinue the treatment, except in case of obvious patient benefit at the criteria of the Investigator and upon agreement with the Sponsor.

**In Part B, patients assigned to Sequence 2 (RT) (lorbinecetin + itraconazole in Cycle 2),** criteria for treatment continuation should be investigated on Day 15 of Cycle 1 in order to confirm itraconazole administration start on Day -4 of Cycle 2, assuring that the continuation criteria will be finally met on Day 1 of Cycle 2 assessment. In case of detected abnormalities on Day 15 in sequence RT, these assessments should be repeated every 48-72 hours until recovery to retreatment criteria. Initiation of itraconazole will be delayed for a maximum of 14 days to ensure that pre-treatment with itraconazole is fulfilled. If recovery has not occurred after that period, the patient should discontinue the treatment, except in case of obvious patient benefit at the criteria of the Investigator and upon agreement with the Sponsor.

Re-treatment criteria for lorbinecetin administration should be met on Day 1 of Cycle 2.

Any patient having any grade  $\geq 3$  laboratory abnormalities and/or treatment-related AEs after Cycle 2 or Cycle 3 is suggested to have the relevant tests re-assessed at intervals of at least 72 hours but not more than one week.

If they were not met, treatment will be delayed for a maximum of 2 days to evaluate continuation of lorbinecetin administration, with re-treatment criteria being checked every 24 hours. During this time the patient will continue receiving itraconazole. If

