### 9.1 ANALYSIS POPULATIONS

The PK population will include all patients enrolled in Part A and B who have sufficient and interpretable PK parameters to calculate the non-compartmental PK parameters. Only the patients in Part B who have completed the two cycles and have sufficient and interpretable PK assessments will be included in the statistical comparison to assess the effect of itraconazole on the PK of lubrinezdin.

The safety population will include all patients who received at least one dose of lubrinezdin. Patients who have received at least one dose of itraconazole but who did not receive any dose of lubrinezdin will be excluded from the safety population. The analysis of data from these patients will be performed separately (e.g., by means of narratives). The safety population will be used for all safety evaluations.

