## 2 OVERALL STUDY DESIGN

This is a prospective, open-label, two-way crossover, phase Ib drug-drug interaction study in patients with advanced solid tumors.

The study will include a pre-treatment (screening) phase (within 14 days before the first lurbinectedin or itraconazole administration) followed by a treatment phase consisting of two lurbinectedin cycles, one cycle in combination with itraconazole and one cycle of lurbinectedin as single agent (in different order depending on the study sequence), and one additional third cycle of lurbinectedin as a single agent for patients who meet the continuation criteria and obtain a clinical benefit after the first two cycles, and then follow-up of adverse events if any.

Patients who meet the continuation criteria and obtain a clinical benefit according to the Investigator's criteria will have the opportunity to continue treatment under a Compassionate Use Agreement after the completion of the optional third study cycle.

[figure not shown]
Patients will be treated as outpatients. At the discretion of the Investigator, patients may be admitted to the study center on Day -1 or Day 1 and monitored, at least, until completion of the Day 1 PK blood sample collections.

Patients will receive a maximum of three cycles: two consecutive cycles of lurbinectedin, one cycle with and one cycle without itraconazole co-administration (in different order depending on the study Sequence 1 or Sequence 2 of treatment), followed by a third cycle with lurbinectedin alone (this last optional for patients with clinical benefit). Lurbinectedin will be administered as a 1-hour (-5/+20 min) i.v. infusion q3wk via a central or peripheral vein.

In the co-administration cycles, itraconazole will be administered orally once daily in the morning after breakfast during 12 consecutive days, self-administered at home from Day -4 (i.e., four days before lurbinectedin infusion) until Day 8 (i.e., seven days after lurbinectedin infusion), and supplied at the study center on Day 1, following recommendations at the Summary of Product Characteristics (SmPC). On Day 1 (i.e., the day of lurbinectedin infusion), itraconazole will be given immediately prior to starting the lurbinectedin infusion. In fact, itraconazole should be administered after obtain the itraconazole PK sample #1 and before the start of lurbinectedin infusion (-15 min to -1 min).

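### In Sequence 1 the conditional repeat of older screening and pregnancy tests is timed to the lurbinectedin infusion, so three or four itraconazole doses can come before it

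*Protocol*

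**What the plan says.** **Repeat rule.** In the Sequence 1 (TR) schedule, the permitted windows before Day 1 of Cycle 1 state for the pregnancy test: "If pregnancy test was done >7 days before Day 1 of Cycle 1, the test must be repeated the day before or" on Day 1. Physical examination, ECOG PS, vital signs, hematology, biochemistry, creatinine clearance and coagulation are repeated if they "were assessed >10 days before Day 1 of Cycle 1, the tests must be repeated the day before or the Day 1". Both repeats must precede lurbinectedin. The same text stands under Tables 4 and 5. Footnote a of the schedule uses the same anchor: "Should treatment be administered more than ten days after the screening tests, repeat these tests prior to the first infusion".

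**First study drug.** Protocol 7.2 has itraconazole "self-administered at home from Day -4 (i.e., four days before lurbinectedin infusion". In Sequence 1 this falls in Cycle 1. Protocol 5.2 starts the treatment period with the first dose of either drug.

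**Eligibility at treatment.** Protocol 6.2: "A patient should only be treated if eligibility criteria are still met according to assessments performed closest to first drug administration". The window text closes with a similar sentence tied to treatment start.

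**Screening window.** The protocol allows 14 days before registration (4.1 criterion 7; Table 4). SAP section 2 describes a screening phase "within 14 days before the first lurbinectedin or itraconazole administration".

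**The concern.** The repeat rule exists so that nobody is treated on old results. In Sequence 1 it protects the lurbinectedin infusion but not the first study drug. The schedule places no eligibility or pregnancy test on Days -4 to -2, so someone who has become ineligible since screening, including through pregnancy (exclusion criterion 6), may be taking study drug before the mandatory re-check. Footnote j shows that the protocol foresees a failed check on Day 1 of Cycle 1 in this sequence, with itraconazole already under way.

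The stake is mainly patient protection. There is also a smaller operational cost. Protocol 9.1 removes from the safety population "Patients who have received at least one dose of itraconazole but who did not receive any dose of" lurbinectedin and describes them separately, and 5.3 requires non-evaluable patients to be replaced. Eight evaluable Part B patients carry the primary comparison, so an avoidable loss matters.

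**Working it through.** **1. Dose count, reproducing the stated course length.** There is no Day 0. Days -4 to -1 give 4 doses and Days 1 to 8 give 8. The total is 4 + 8 = 12, as 7.2 states; with the two-day delay it is 14, also as stated.

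**2. Doses before the repeat.**

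| Repeat done | Itraconazole doses already taken |
|---|---|
| Day -1, before the morning dose | 3 |
| Day -1, after the morning dose | 4 |
| Day 1, before that day's dose | 4 |
| Before the Day -4 dose (if anchored to itraconazole) | 0 |

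**3. Patients.** Sequence 1 has 3 patients from Part A and 8/2 = 4 from Part B, which makes 7 of 11. This is a ceiling: the rule applies only to patients whose tests are more than 10 days old at Day 1, or more than 7 days old for the pregnancy test in women of childbearing potential.

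**4. Oldest result at the first itraconazole dose.** Under the SAP window it is 14 days. Under the protocol window, age at Day -4 = 14 + days from registration to Day -4. The documents do not state that gap, so registration days are assumed:

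| Registration (assumed) | Age at Day -4 | Age at Day 1 |
|---|---|---|
| Day -4 | 14 + 0 = 14 | 18 |
| Day -5 | 14 + 1 = 15 | 19 |
| Day -7 | 14 + 3 = 17 | 21 |

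**5. Youngest result that triggers a repeat.** Pregnancy: 8 days at Day 1, so 8 - 4 = 4 days at Day -4. Other tests: 11 days at Day 1, so 11 - 4 = 7 days at Day -4. Pregnancy tests done 8 to 11 days before Day 1, and other tests done 11 to 14 days before, are thus still within 7 and 10 days when counted to Day -4. Older ones exceed the limit on either count.

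**6. The passages together.** Treatment starts on Day -4 (5.2). Eligibility must hold on the assessments nearest to first drug administration (6.2). The only mandated fresh assessment comes on Day -1 or Day 1. Neither 6.2 nor the closing sentence of the window text orders a test, so the nearest result before Day -4 can be the screening result itself.

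**The case against.** The strongest reply is that there is no formal contradiction. Section 6.2 sets no age limit and can be met by the screening result. The 7- and 10-day limits are defined to Day 1 of Cycle 1, not to itraconazole, and timing the re-check to the cytotoxic infusion is a defensible priority. This stands in part: 6.2 is not breached outright, and step 5 shows that some results which trigger a repeat are recent enough at Day -4. It does not explain why a rule tied to treatment start should operate only after treatment, as the protocol defines it, has begun.

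A reader might infer more, and the documents do not support it:

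- *Losses after randomization in Sequence 1 only.* Sequence 2 has the same Day -1/Day 1 re-check before Cycle 1, so its patients can also be lost after randomization. It can lose others at Day 1 of Cycle 2. Part A is not randomized, and replacements go to the same sequence. What is particular to Sequence 1 is failing the Cycle 1 re-check after exposure to itraconazole.
- *Sequence 2 already has an equivalent safeguard.* Under 7.4, "criteria for treatment continuation should be investigated on Day 15 of Cycle 1 in order to confirm itraconazole administration start on Day -4". That check covers the continuation criteria in Table 7, which do not include pregnancy. The Sequence 2 pregnancy test is scheduled on Day 1 of Cycle 2 (one day earlier allowed), also after itraconazole has started.
- *Itraconazole distorts the liver tests used for the decision.* Protocol 3.2 reports mild, transient elevations in under 5% of patients on chronic dosing and calls the liver-injury risk of courses up to 14 days very low. Nothing shows that three or four doses shift the Day 1 check.

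**Conclusion.** The point holds as a mismatch of anchors. In Sequence 1 a patient with older screening results can take three or four itraconazole doses before the re-check the protocol requires. At most 7 of 11 planned patients are exposed to this, fewer in practice. The oldest result at the first dose is 14 days under the SAP, or 14 to 17 days under the protocol if registration falls on Day -4 to Day -7, which is an assumption. The two documents also anchor the screening window differently. No bias in the treatment comparison is shown, and the sample size and analysis model are untouched.

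**What to change.** Reconcile the permitted-window text (Sequence 1 schedule, Tables 4 and 5), footnote a and the Table 5 timing entries with protocol 5.2 and 6.2 and SAP section 2:

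- In Sequence 1, also count the age of screening results to the first itraconazole dose. Any repeat then due is done and reviewed at or before the existing delivery contact (Day -7 to Day -4, footnote h), before the first capsule is taken.
- Keep the Day -1/Day 1 repeat, triggered by the date of the screening test. Otherwise an early repeat would cancel it: a test on Day -7 is 7 days old at Day 1 and meets neither the more-than-7 nor the more-than-10-day condition.
- State one screening window in both documents, including the interval from registration to first dose.
- Address in the same revision the pregnancy test in Sequence 2 Cycle 2.

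What follows clinically from a failed check is for the sponsor to settle.

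The cost is wording, plus one additional blood draw at an existing contact (with the examination items on the same list), only for patients with older results. If delivery is on Day -4 itself, results are needed before that morning's dose, so an earlier day in the window is more practical. No new type of test is needed.
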